- 7) This patient will be readmitted to the hospital in the next 3 months
- 8) This patient will die during the next 3 months

Safety

The greatest risk in administering a diuretic is the potential to make the patient volume depleted via diuresis. In order to ensure that this does not happen, the urine output after the furosemide bolus will be matched ml for ml with isotonic saline. The treating team has the option of replacing less isotonic saline if the treating team wants volume to be removed. However, the default procedure will conduct this matched replacement for six hours after the furosemide bolus. Since furosemide induces the production of hypotonic urine, a milliliter for milliliter matched repletion of normal saline guarantees that the patient cannot become volume depleted.

Furosemide is routinely given to patients with AKI, particularly those with acute tubular necrosis. Furosemide has not been shown to be harmful nor helpful in patients suffering from AKI despite its widespread use in patients with acute and chronic kidney disease. Because we are excluding patients who are pre-renal, we are minimizing the risk of volume depletion.

Sample Size:

The study team aims to enroll 200 patients with AKI.

First and foremost we are looking to determine if we can replicate the success of our pilot data in a larger multi-center investigation. In powering the overall validation study we assumed 80% power and 5% alpha with this analysis being performed using SAS, Cary, NC, USA. [14] We used a conservative approximation to the variance that assumes independence of the binary variables to calculate power. To investigate the utility of the FST to predict the progression from Stage 1 AKI to Stage 3 we have provided a **Table 6** which demonstrates the change in the True Positive Rate (ΔTPR) based on the event rate and the risk threshold for defining high risk. Recall that the TPR is equivalent to the number of True Positives divided by the True Positives plus the False Negatives ($\text{TPR} = (\text{TP})/(\text{TP}+\text{FN})$) and that this is the equivalent of McNemar's test. [15] Moreover it is important to note that ΔTPR is the equivalent of the Net Reclassification

Index (NRI) for those with the event (Progression to Stage 3 AKI). Practically, this same Table

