demonstrates the minimum detectable change in the False Positive Rate (ΔFPR). The FPR is the number of False Positives divided by the false positives plus the True Negatives ($\text{FPR} = ((\text{FP})/(\text{FP}+\text{TN}))$). Additionally, the $\text{FPR} = 1 - \text{Specificity}$ and perhaps more importantly, ΔFPR is

Table 2 - Detectable change in the Percentage of cases classified as high risk by adding biomarkers to the clinical model.					
Total Sample Size	Event Rate	Expected Number of AKI Progressors (Cases)	10% Classified as High Risk without biomarker	20% Classified as High Risk without Biomarker	50% Classified as High risk Without biomarker
150	15%	22.5	0.21	0.30	0.36
150	30%	45	0.16	0.20	0.26
150	45%	67.5	0.13	0.17	0.22
200	15%	30	0.20	0.28	0.34
200	30%	60	0.15	0.19	0.25
200	45%	90	0.12	0.16	0.20
250	15%	37.5	0.19	0.26	0.32
250	30%	75	0.14	0.18	0.23
250	45%	112.5	0.11	0.15	0.19
300	15%	45	0.18	0.24	0.30
300	30%	90	0.13	0.17	0.21
300	45%	135	0.10	0.14	0.17

equivalent to the NRI
Non Event (non-
progression to Stage 3).
Thus one could look at
Table 6 and view these
numbers as the NRI for
Non-Events.

For the
purpose of this
analysis we have
varied the cohort
sample size as well as
the event rate
(progression). Event
rate variation accounts
for the limited data on
progressive AKI in the

existing literature. While our pilot data (n=77) demonstrated an event rate 32% [11], previously published studies have had varied rates from TRIBE AKI's (13%) [16], EARLY-ARF's (33%) [17] and Siew's et al (29%) [18]. As such a rate progression rate of 30% seems appropriate. To interpret Table 2 if we assume we have 200 individuals with a 30% AKI progression rate (60 cases /AKI progressors) we will be able to detect improvements of 0.15-0.25 in the % of cases classified as high risk (Δ TPR=NRI events). Inversely, for the same cohort and event rate we would be able to detect identical improvements in the Δ FPR (= NRI for non-events). **Thus with 200 subjects and a 30% event rate we would be able to detect small to medium sized improvements in reclassification (NRI events + NRI non-events =Total NRI 0.30-0.50)[19]**

Endpoints and Definitions

AKI – an increase in serum creatinine of >0.3 mg/dL or 50% increase from baseline over 48 hours or an increase to greater than or equal to 150 to 200 percent from baseline or sustained oliguria (mean output of <0.5 cc/kg/hr for 6 hours).

Non-renal recovery

- (1) Patients who require RRT within 14d of enrollment

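### Table 2 does not come from one calculation: 45 cases get two answers, 0.19 in the planned row is not reproduced, and the false-positive claim ignores the 140 non-events

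*Combined protocol and SAP*

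**What the plan says.** All of this is in section D, Sample Size, of the combined protocol and SAP.

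- Design values: "In powering the overall validation study we assumed 80% power and 5% alpha". Sidedness is not given.
- Variance: "We used a conservative approximation to the variance that assumes independence of the binary variables to calculate power". No formula is written out.
- Test: after defining the true positive rate (TPR) as TP/(TP+FN), the text says "that this is the equivalent of McNemar"'s test.
- Table 2 is titled "Detectable change in the Percentage of cases classified as high risk by adding biomarkers to the clinical model". Its rows are total sample size by event rate. Its columns are the percentage classified as high risk without the biomarker (10%, 20%, 50%).
- Planned row: "if we assume we have 200 individuals with a 30% AKI progression rate (60 cases /AKI progressors", with entries 0.15/0.19/0.25. The text concludes "we will be able to detect improvements of 0.15-0.25 in the % of cases classified as high risk".
- Non-events: the table also "demonstrates the minimum detectable change in the False Positive Rate" (FPR), and "for the same cohort and event rate we would be able to detect identical improvements in the" FPR. The two ranges are then added to give a total NRI of 0.30-0.50.

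The Statistical Analysis section makes the NRI the primary analysis and refers back to this section, which holds the only power statement in the plan.

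**The concern.** A change in TPR is estimated among cases alone. At fixed power, alpha, correlation and baseline percentage, the detectable change therefore depends only on the number of cases. Rows with the same number of cases must agree, whatever the total sample size, and in Table 2 they do not. The planned row belongs to the part of the table that fails to reproduce.

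An FPR is estimated among non-events. Table 2 is indexed by cases, so it can serve for FPR only if the two groups are the same size, that is, at a 50% event rate. The planned row assumes 30%.

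At stake is whether the detectable effects quoted for the primary analysis follow from the stated assumptions.

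**Working it through.** **Inputs.** 80% power and 5% alpha, independence of the two classifications, and the Table 2 entries are from the plan. Cases in the planned row: 200 × 0.30 = 60. Non-events: 200 − 60 = 140. Assumption: two-sided alpha, so z = 1.960 + 0.842 = 2.802.

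**1. Rows with equal case counts**

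| Cases | Row | 10% | 20% | 50% |
|---|---|---|---|---|
| 45 | N=150, 30% | 0.16 | 0.20 | 0.26 |
| 45 | N=300, 15% | 0.18 | 0.24 | 0.30 |
| 90 | N=200, 45% | 0.12 | 0.16 | 0.20 |
| 90 | N=300, 30% | 0.13 | 0.17 | 0.21 |

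The 45-case rows differ by 0.02, 0.04 and 0.04, which two-decimal rounding cannot produce. The 90-case rows differ by 0.01 throughout.

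**2. Reproducing the table.** The plan gives no formula. The simplest one under independence is

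d = 2.802 × √(2p(1−p)/cases), with p the baseline percentage.

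- 45 cases: 0.177/0.236/0.295, which matches the N=300 row only.
- 90 cases: 0.125/0.167/0.209. Rounded, this is the N=300 row; truncated, it is the N=200 row.
- Matches to two decimals: N=300, 9 of 9; N=250, 9 of 9; N=200, 1 of 9; N=150, 0 of 9.
- All 18 entries for N=150 and N=200 lie below the unrounded formula value, so they err on the favourable side.
- With one-sided alpha, none of the 18 cells for N=250 and N=300 match, which supports the two-sided reading.

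A possible source, by inference only: 15 of the 18 entries for N=150 and N=200 extend the step from N=300 to N=250 in a straight line, although the detectable change scales with 1/√n.

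**3. Planned row on that formula (60 cases)**

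- 10%: 2.802 × √(0.18/60) = 0.153, stated 0.15.
- 20%: 2.802 × √(0.32/60) = 0.205, stated 0.19.
- 50%: 2.802 × √(0.50/60) = 0.256, stated 0.25.

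Power at the stated values is Φ(d/√(2p(1−p)/60) − 1.96):

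- 0.15: Φ(2.739 − 1.96) = 78%.
- 0.19: Φ(2.602 − 1.96) = 74%.
- 0.25: Φ(2.739 − 1.96) = 78%.

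**4. Including the post-biomarker rate, q = p + d, under independence.** The formula in step 2 uses the baseline rate twice. The variance terms become:

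- 10%: 0.10×0.90 + 0.25×0.75 = 0.2775, against 0.18 (ratio 1.54).
- 20%: 0.20×0.80 + 0.39×0.61 = 0.3979, against 0.32 (ratio 1.24).
- 50%: 0.50×0.50 + 0.75×0.25 = 0.4375, against 0.50 (ratio 0.88).

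Unpooled power is Φ(d/√([p(1−p)+q(1−q)]/60) − 1.96). McNemar power is Φ((d√60 − 1.96√ψ)/√(ψ − d²)), with ψ = p(1−q) + q(1−p) = 0.300, 0.434 and 0.500.

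| | 10% (0.15) | 20% (0.19) | 50% (0.25) |
|---|---|---|---|
| Power, unpooled | 60% | 65% | 83% |
| Power, McNemar | 57% | 61% | 80% |
| Detectable at 80%, unpooled | 0.198 | 0.230 | 0.241 |
| Detectable at 80%, McNemar | 0.209 | 0.242 | 0.251 |

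**5. FPR with 140 non-events.** The step 2 formula gives 0.100/0.134/0.167, not 0.15/0.19/0.25. For a fall in FPR with the post-biomarker rate included, and the column percentage read as the baseline FPR (an assumption), the detectable falls are 0.079-0.080/0.115-0.117/0.163-0.166. On that reading, a fall of 0.15 from 10% is impossible.

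**The case against.** **The formulas are the reviewer's, not the plan's.** This is true. The plan says that it used an approximation and gives no formula. But the conflict between the 45-case rows needs no formula. The step 2 formula earns its place by reproducing 18 of 18 cells in half of the table. The 57-65% figures do rest on a variance that the plan does not state. They show that the word conservative does not hold in the 10% and 20% columns; they do not show a slip in a formula the plan wrote down.

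**Most of the planned row is close.** On the step 2 formula, 0.15 and 0.25 have the same 78% power and are rounding-level misses. Only 0.19 clearly misses. The 90-case rows are weak evidence, because rounding against truncation of one result could explain them.

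**Sidedness is unstated.** One-sided 5% would give 86/83/86% on the step 2 formula, but it does not reproduce the table. With the post-biomarker rate included, one-sided power is still only 69-71% for 0.15 and 73-75% for 0.19.

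**Independence is a worst case.** This stands. The same patients are classified twice, so positive correlation is plausible and would raise power. A correlation of about 0.41-0.47 (10% column) or 0.31-0.38 (20% column) would restore 80%. The plan states none.

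**Stronger readings.** A reader might infer that the study is underpowered or that the total NRI is overstated. The documents support neither. The first fails because of the correlation point above. On the second, adding two separate detectable values is not a power calculation for the total, and the FPR part is too pessimistic where it is feasible. A proper figure needs baseline high-risk rates in cases and in non-cases, and the plan does not give them separately.

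**Conclusion.** The power statement behind the primary analysis is wrong as written.

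- Table 2 contradicts itself for 45 cases, by up to 0.04. Its N=150 and N=200 rows do not follow from the calculation that reproduces the rest.
- In the planned row, 0.19 has 74% power on that calculation, while 0.15 and 0.25 are near misses at 78%.
- With the post-biomarker rate included, 0.15 and 0.19 fall to about 57-60% and 61-65%. The value 0.25 is supported at about 80-83% with asymptotic tests; exact McNemar gives about 75%.
- Equal detectability for FPR does not follow from 140 non-events. That error is conservative, except that a 0.15 fall is impossible if 10% is the baseline FPR.

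The power figures assume two-sided 5% and the plan's independence; the conflict between the 45-case rows needs neither. The fault is in the stated calculation, and nothing here calls for more than 200 patients.

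**What to change.** 1. Recompute all of Table 2 from the number of cases, with one written formula that includes the post-biomarker rate. State the sidedness and any correlation assumed. Under independence and two-sided 5%, the planned row becomes about 0.20-0.21/0.23-0.24/0.24-0.25. If a smaller value is kept, state the correlation that supports it.
2. Replace the claim of equal FPR improvements with a separate calculation on 140 non-events and a stated baseline FPR. If the column percentages are that baseline, the detectable falls are about 0.08/0.12/0.16-0.17.
3. Remove the total NRI of 0.30-0.50 as a sum of two detectable values, or recompute it as a single test with the sponsor's own baseline rates in cases and non-cases.

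The cost is one table and a few sentences, with no change to enrolment or procedures. The downside is that the lower end of the detectable change in TPR moves from 0.15 to about 0.20.

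### The detectable change in false-positive rate is read from a table computed on progressors, and two minimum detectable changes are added to give a Total NRI of 0.30-0.50

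*Combined protocol and SAP*

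**What the plan says.** All of this stands in section D, Sample Size, unless noted.

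- **Power basis.** "In powering the overall validation study we assumed 80% power and 5% alpha". Sidedness is not stated. On variance: "We used a conservative approximation to the variance that assumes independence of the binary variables to calculate power".
- **What the table measures.** Table 2 (called Table 6 in parts of the text) is headed "Detectable change in the Percentage of cases classified as high risk by adding biomarkers to the clinical model". Each row lists the expected number of progressors. The three value columns assume that 10%, 20% or 50% are already high risk without the biomarker.
- **Reuse for FPR.** The same table is said to be one that "demonstrates the minimum detectable change in the False Positive Rate", and its entries may be viewed as the NRI for non-events. FPR is defined there as FP/(FP+TN).
- **Worked example.** It takes "200 individuals with a 30% AKI progression rate (60 cases /AKI progressors" and reads off 0.15-0.25 for the change in true-positive rate (TPR). It continues: "Inversely, for the same cohort and event rate we would be able to detect identical improvements in the" FPR.
- **Conclusion.** The study is said to be able to "detect small to medium sized improvements in reclassification (NRI events + NRI non-events =Total NRI 0.30-0.50".

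The Statistical Analysis section makes the NRI the basis of the primary analysis and refers back to this text.

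**The concern.** There are two separate faults.

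1. **Wrong denominator.** A change in TPR is estimated in progressors and a change in FPR in non-progressors. At 200 patients and 30% events these groups have 60 and 140 members, so one row cannot give the minimum for both. Because the plan specifies the same cohort and event rate, the reader is not being sent to another row.
2. **Adding minimums.** The total range is 0.15 + 0.15 to 0.25 + 0.25. The two groups are independent, so their variances add, and the smallest detectable sum is less than the sum of the two smallest detectable components.

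This paragraph is the plan's only statement of what the primary analysis can detect. If it is wrong, a reader cannot tell which non-event NRI or total NRI the study has 80% power for.

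**Working it through.** **Inputs from the plan:** 80% power; 5% alpha; independent classifications; N = 200; event rate 30%; baseline shares p = 10%, 20%, 50%. **Assumptions:** two-sided alpha, and the same baseline shares applied to non-progressors, for whom the plan gives none.

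Non-progressors: 200 × 0.70 = 140. At event rates of 15% and 45%: 170 and 110.

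**1. Reproducing the table.** With z = 1.960 + 0.842 = 2.802 and baseline-only variance, the minimum detectable change is 2.802 × √(2p(1−p)/n), where n is the number of progressors. This matches all 18 cells of the N = 250 and N = 300 rows to two decimals, so those rows are driven by case counts. At n = 60 it gives 0.153 / 0.205 / 0.256 against the printed 0.15 / 0.19 / 0.25. The N = 150 and N = 200 rows do not follow the formula throughout, and equal case counts carry different values:

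| Cases | Smaller N | N = 300 |
|---|---|---|
| 45 | 0.16 / 0.20 / 0.26 (N = 150) | 0.18 / 0.24 / 0.30 |
| 90 | 0.12 / 0.16 / 0.20 (N = 200) | 0.13 / 0.17 / 0.21 |

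The printed event cells are therefore not used as inputs below.

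**2. Impossible cells (no variance assumption).** An FPR improvement is a fall and cannot exceed its baseline. If the columns are read as baseline FPR, 11 of 12 cells in the 10% column exceed 0.10. In the 20% column 4 of 12 exceed 0.20 (0.30, 0.28, 0.26, 0.24), and in the 50% column none exceeds 0.50. That makes 15 of 36 cells impossible, including the 0.15 used in the worked example.

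**3. Trend.** At N = 200 the 10% column falls from 0.20 to 0.12 as the event rate rises from 15% to 45%. Non-progressors drop from 170 to 110, so the detectable FPR change must rise.

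**4. FPR on 140 non-progressors.** Let q = p − d. Under independence the discordance is D = q(1−p) + p(1−q), and the variance under the alternative is D − d². The McNemar condition is d√n = 1.960√D + 0.842√(D − d²). Check at p = 20%, d = 0.117: q = 0.083, D = 0.2498, D − d² = 0.2361, and the right side divided by √140 is 0.117.

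| Detectable FPR fall | 10% | 20% | 50% |
|---|---|---|---|
| McNemar, n = 170 | 0.074 | 0.108 | 0.151 |
| McNemar, n = 140 | 0.080 | 0.117 | 0.166 |
| McNemar, n = 110 | 0.088 | 0.130 | 0.187 |
| Baseline-only, n = 140 | 0.100 | 0.134 | 0.167 |
| Stated in the plan | 0.15 | 0.19 | 0.25 |

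Table 2's own row nearest 140 subjects, "300 45% 135 0.10 0.14 0.17", agrees with the baseline-only line and not with the stated values. Simulated McNemar power with n = 140 is above 99.9% for a fall of 0.10 from 10% (the largest possible), above 99.9% for 0.19 from 20%, and 99% for 0.25 from 50%.

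**5. Total NRI.** SE = √(V_events/60 + V_non-events/140), with each V = D − d² under the alternative. Example at p = 50%, total 0.30 split evenly: D = 0.50 in both groups, V = 0.50 − 0.15² = 0.4775, SE = √(0.4775/60 + 0.4775/140) = 0.1066, and 2.802 × 0.1066 = 0.299.

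| 80%-power Total NRI | 10% | 20% | 50% |
|---|---|---|---|
| Even split, alternative variance / McNemar-type | 0.194 / 0.198 | 0.250 / 0.254 | 0.299 / 0.304 |
| All in events, same two tests | 0.225 / 0.237 | 0.267 / 0.280 | 0.288 / 0.300 |
| Stated (sum) | 0.30 | 0.38 | 0.50 |

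Simulated power at the stated totals is 98% for 0.30 at 10% (as +0.20 and −0.10, since −0.15 is impossible), 99% for 0.38 at 20%, and 99.8% for 0.50 at 50%. With an even split, totals of 0.25 at 20% and 0.30 at 50% give about 80%.

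**The case against.** - **The sentences are literally true where attainable.** A study with 98% power or more for a change is able to detect it, and the word for minimum appears only in the general sentence about the table. This stands as far as it goes: both errors are on the safe side. It does not rescue a claim of identical detectable changes under a stated 80% power, or a fall of 0.15 from 10%.
- **The total may be only an identity.** Event NRI plus non-event NRI does equal total NRI, and the plan does not say which of the three is tested. The combined standard error matters only if the total is tested or its detectability is claimed, and the concluding sentence of the section does claim it.
- **The 10%, 20% and 50% columns are defined for cases.** Correct: the impossible-cell count depends on reading them as baseline FPR. The plan invites that reading by offering the table for FPR. The denominator argument and the trend check do not need it.
- **The table's baseline-only variance should be kept.** For the FPR this matters little (0.10 / 0.13 / 0.17). For the total it gives 0.183 at 10%, which reaches only about 76% power with an even split, so variance under the alternative is the better choice.
- **The replacement totals rest on undocumented splits and baselines.** This stands. A split weighted to non-events gives about 0.24 at 20%, just outside the range shown. The totals are a check on a recalculation and not text for the protocol.

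**Conclusion.** The point holds. For 200 patients and 30% events, the stated detectable FPR changes of 0.15 / 0.19 / 0.25 are not 80%-power minimums. On 140 non-progressors the figures are about 0.08-0.10, 0.12-0.13 and 0.17. The Total NRI of 0.30-0.50 is a sum of two minimums. The 80%-power total is about 0.19-0.24, 0.25-0.28 and 0.30 at the three baselines, for splits from even to all in events.

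These figures assume two-sided 5% alpha, independence and equal baseline shares in both groups. With one-sided alpha the totals fall to about 0.17-0.20, 0.22-0.25 and 0.26-0.27. Positive correlation between the two classifications would lower all of them. The wrong denominator and the non-additivity do not depend on these choices.

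For the non-event and total figures the error is conservative. It does not show that the sample is too small, and it changes no endpoint or procedure. No conclusion is drawn here about the 0.15-0.25 range for events. The point should be fixed because the primary analysis takes its stated targets from this paragraph.

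**What to change.** 1. Remove the claim that the FPR changes are identical, and the statements that the table gives the detectable FPR change and can be viewed as the NRI for non-events. Alternatively, add FPR columns computed on N × (1 − event rate), with baseline shares stated for non-progressors.
2. Replace the total of 0.30-0.50 with a value from SE = √(SE_events² + SE_non-events²), with variance evaluated under the alternative. Suggested wording: *With 60 progressors and 140 non-progressors, 80% power and [one/two]-sided 5% alpha, the minimum detectable Total NRI is [x], assuming that [a]% of progressors and [b]% of non-progressors are high risk without the biomarker, a split of [c] in events and [d] in non-events, and independence of the two classifications.*
3. Regenerate Table 2 from one stated formula before using its cells, since 45 and 90 cases each carry two sets of values.

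The cost is a recalculated paragraph and some table columns. Design and sample size do not change.

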- (2) Patients who die before 14d, and whose serum creatinine remains >2.0 mg/dl over baseline creatinine at the time of death
- (3) Patients who die before 14d and whose urine output is less than 400cc/24 hours at the time of death

Renal Recovery

- (1) Patients who do not require RRT and survive 14d or are discharged prior to 14 days
- (2) Patients who die before 14d with a serum creatinine >2.0 mg/dl above their baseline AND with a urine output >400cc/24 hours

Statistical Analysis

Patients will be followed for 30 days or until hospital discharge, whichever occurs first. Need for dialysis, serum creatinine, urine output, medication regimens, and mortality will be assessed. Primary analysis will be based on the net reclassification index as discussed in the sample size section above, additionally we will look at the more traditional receiver operating characteristics (ROC) of urine output and urinary sediment score and biomarkers after furosemide challenge to predict AKI progression. Additionally, time to AKI progression and renal recovery/non-recovery will be assessed. Patient outcomes will be stratified by entry criteria and baseline renal function. We will be looking at the long term, (3 year) outcomes in this cohort as well. However given the focus of this study is to identify severe AKI early in the clinical course and that rates of morbidity and mortality in our ICU- AKI cohort are extremely high, we are not sufficiently powered to look at long term outcomes and this aspect of the study is somewhat exploratory and will serve as pilot data for future studies.

Study Procedures

1. Identify appropriate patients via inclusion/exclusion
2. Consent patient or legal representative
3. Draw 7cc of blood, collect 50cc of fresh urine
4. Bolus dose of furosemide
5. Assess urine output response over the next 6 hours
6. Match urine output with intravenous isotonic saline, 1 ml for 1 ml for 6 hours (at the discretion of the clinically treating team – if they feel diuresis is needed clinically they can decide to hold the intravenous fluids – this has not changed from prior submission)
7. Draw 7cc of blood, collect 50cc of fresh urine 2 hours after the furosemide
8. Draw 7 cc of blood; and another 50cc of urine the following morning at 24 hours post dose
9. Draw 7 cc of blood; and another 50cc of urine at the time of ICU discharge
10. Draw 7 cc of blood; and another 50cc of urine at the time of hospital discharge

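### The non-event part of the primary NRI is written without its minus sign, and if a fall in FPR was meant, the lower end (0.30) of the stated detectable range cannot occur

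*Combined protocol and SAP*

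**What the plan says.** All the relevant text is in section D of the combined protocol and SAP.

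- **Sample Size, events.** TPR is TP/(TP+FN), and "ΔTPR is the equivalent of the Net Reclassification" Index among patients who progress to Stage 3.
- **Sample Size, non-events.** FPR is FP/(FP+TN), stated to equal one minus specificity. ΔFPR is equated with the non-event NRI twice: in the text beside Table 2, which invites the reader to take the table's entries as non-event NRIs, and in the worked interpretation, which promises "identical improvements in the Δ FPR (= NRI for non-events"). Neither place has a minus sign.
- **Sample Size, total.** For "200 individuals with a 30% AKI progression rate (60 cases /AKI progressors"), the detectable ΔTPR is 0.15 to 0.25, and the conclusion is "NRI events + NRI non-events =Total NRI 0.30-0.50".
- **Table 2.** Its title concerns the percentage of cases classified as high risk. The entries at N = 200 and 30% are 0.15, 0.19 and 0.25, for 10%, 20% and 50% classified high risk without the biomarker.
- **Statistical Analysis.** "Primary analysis will be based on the net reclassification index as discussed in the sample size section above". No formula is given there.

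**The concern.** With FPR equal to one minus specificity, a rise in FPR is a loss. The non-event NRI is the share of non-events moved down minus the share moved up, which is FPR without the marker minus FPR with it. The document equates it with ΔFPR and then adds the two NRI parts. Substituting the stated definitions gives ΔTPR + ΔFPR, where the index should be ΔTPR - ΔFPR.

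This text is the only specification of the primary index. An analyst who coded it as written would credit false positives and debit gains in specificity. An analyst who assumed the usual sign would get a different number from the same data. The choice should not be left open until the data are in hand.

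The planned range is also affected. A table of changes in the share of cases called high risk is reused, unchanged, as a table of improvements in FPR. Those improvements run in the opposite direction, are bounded by the starting FPR, and arise in a group of a different size.

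**Working it through.** **Inputs.** From Sample Size: 80% power, 5% alpha ("we assumed 80% power and 5% alpha"; sidedness not stated, two-sided assumed here), N = 200, 30% event rate, 60 events. Hence 200 - 60 = 140 non-events, a number the document does not state. From Table 2: ΔTPR of 0.15 / 0.19 / 0.25 at baselines of 10% / 20% / 50%. Variance: "We used a conservative approximation to the variance that assumes independence of the binary variables to calculate power"; the exact formula is not given.

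**1. Reproducing the plan's range.** 0.15 + 0.15 = 0.30 and 0.25 + 0.25 = 0.50, so the total is each case figure doubled. For the cells themselves, d = (1.960 + 0.842) × sqrt(2p(1-p)/n) with n = 60 gives 0.153 / 0.205 / 0.256. The end columns agree closely with 0.15 and 0.25; the 20% cell (0.19) does not. Over all of Table 2 this formula matches 19 of 36 cells to within 0.005. The other variants tried match 5 or fewer. The range is therefore reproduced, but the table only in part.

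**2. The sign, if coded literally.**

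| Marker's effect | ΔTPR + ΔFPR (as written) | ΔTPR - ΔFPR |
|---|---|---|
| TPR +0.15, FPR +0.15 | +0.30 | 0.00 |
| Everyone labelled high risk, from 10% | 0.90 + 0.90 = +1.80 | 0.00 |
| TPR +0.19, FPR -0.19 | 0.00 | +0.38 |

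**3. The intended reading, a fall in FPR.** Subtract each N = 200, 30% entry from its baseline:

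- 10% column: 0.10 - 0.15 = -0.05, impossible.
- 20% column: 0.20 - 0.19 = 0.01, possible.
- 50% column: 0.50 - 0.25 = 0.25, possible.

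The 0.15 that produces 0.30 stands only in the column "10% Classified as High Risk without biomarker". It can be a ΔFPR only as a rise from 0.10 to 0.25, which is a worsening. Over the whole table, 11 of 12 entries in the 10% column exceed the largest possible fall and one equals it. In the 20% column 4 exceed it and one equals it. In the 50% column none does.

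**4. Non-event half recomputed for a fall, n = 140.** Two formulas, both two-sided and both under independence:

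- Baseline variance, d = 2.802 × sqrt(2p(1-p)/140): 0.100 / 0.134 / 0.167. At 10% this uses up the whole baseline (0.1005 before rounding), so it is not a usable figure there.
- McNemar, solving n = [1.960 × sqrt(ψ) + 0.842 × sqrt(ψ - d²)]² / d² with ψ = p(1-p+d) + (p-d)(1-p): 0.080 / 0.117 / 0.166.

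Adding the plan's own ΔTPR, as the plan does:

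| Baseline | ΔTPR (plan) | Fall in FPR | Sum | Plan's sum |
|---|---|---|---|---|
| 10% | 0.15 | 0.080 to 0.100 | 0.23 to 0.25 | 0.30 |
| 20% | 0.19 | 0.117 to 0.134 | 0.31 to 0.32 | 0.38 |
| 50% | 0.25 | 0.166 to 0.167 | 0.42 | 0.50 |

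A one-sided 5% test would scale the baseline-variance falls by (1.645 + 0.842)/(1.960 + 0.842) = 0.887, to 0.089 / 0.119 / 0.149. Step 3 does not depend on sidedness or on the variance formula.

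**The case against.** The strongest reply is that the intended direction can be read from the text. The key sentence opens with the word *inversely* and speaks of improvements. Since FPR is defined there as one minus specificity, an improvement can only be a fall. The document never writes ΔTPR + ΔFPR. It adds an event part and a non-event part, which is correct when each part is a gain, and the analysis section names a standard index. If both parts are read as sizes of improvement, the missing sign does not change 0.30-0.50. Finally, Table 2 is titled for cases, so its layout is not itself a mistake.

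Much of this stands. A reader might infer that the sponsor has adopted an index that rewards false positives, or gave no thought to direction. The documents do not support either inference: the wording points the other way, and the wrong result follows only if the stated equality is coded literally. A reader might also treat 0.30 as a limit that the result must clear. It is a detectable effect size, and the plan sets no success limit for the NRI.

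The reply does not rescue the range. Reading the entries as falls is exactly what makes the 10% column impossible. The defect is the reuse of a table built for cases to describe non-events, and it reaches beyond that column, because the 60-case figures are carried over to 140 non-events. Nor does a reader's ability to guess the sign replace a formula for the primary analysis.

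**Conclusion.** The point holds in two limited parts.

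1. The only definition of the primary index equates the non-event NRI with ΔFPR and lacks the minus sign. This is an error of notation in an underspecified definition. Its consequence is conditional: if coded literally, equal rises of 0.15 in TPR and FPR score +0.30 instead of 0, and a marker that improves both rates equally scores 0.
2. On the intended reading, the lower end of the stated detectable total NRI is wrong, because an FPR of 0.10 cannot fall by 0.15. At N = 200 and 30% the 20% and 50% columns do permit the fall, so the impossibility is confined to the 10% column. The upper end is possible, but it borrows a figure for 60 cases.

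The recomputed totals of about 0.23 to 0.42 rest on two-sided testing, on independence of the two classifications, on the same baseline percentage in events and non-events, and on the plan's own ΔTPR figures, which could be reproduced only in part. They indicate size and are not replacement values. For non-events the detectable change is smaller than stated, so this point does not show that the study is too small.

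**What to change.** - In Sample Size, write NRI(non-events) = FPR(clinical model) - FPR(clinical model + marker) and Total NRI = ΔTPR - ΔFPR.
- In Statistical Analysis, cite that formula for the primary analysis and report the event and non-event parts separately as well as the total.
- Delete both statements that let the table serve for non-events: the invitation beside Table 2 (where the text calls it Table 6, although only Table 2 fits) and the claim of identical detectable changes.
- Restate the whole non-event half of 0.30-0.50, not only its lower end, from a calculation for a fall in FPR among the 140 expected non-events. Use baseline FPRs that permit the fall, and state the formula and the sidedness.

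The cost is wording and a short recalculation, with a changed stated range. No patients, procedures or clinical rules are affected. The change should be made before the primary analysis is run, so that the sign is not chosen afterwards.
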